4.0 STUDY DESIGN

4.1 Study Design Overview

This is an open-label, multicenter Phase 1b/2 study to determine the MTD and/or RP2D of ARRY-382 in combination with pembrolizumab in adult patients with selected advanced solid tumors (Part A/Phase 1b); and to estimate the efficacy of the combination in patients with advanced solid tumors that have progressed on prior PD-1/PD-L1 inhibitors, in patients with prOVCA and in patients with PDA (Phase 2).

Each phase of the study consists of a 28-day screening period; 21-day treatment cycles with the combination of ARRY-382 and pembrolizumab until disease progression as determined by the Investigator, unacceptable toxicity, withdrawal of consent, or death (or other discontinuation criteria are met [see also [Section 9.2](#)]); and a 30-day safety follow-up period. Patients in all cohorts/phases will be monitored for OS until 1 year after the date of the last patient's first visit.

Part A (Phase 1b) includes a dose-escalation component with 2 planned dose cohorts ([Table 6](#)). Oral doses of ARRY-382 will be administered QD in combination with pembrolizumab 2 mg/kg iv Q3W. Patients in Cohort 1 will be enrolled on a rolling basis up to 6 evaluable patients or until DLTs (see [Section 4.2](#)) are observed in more than 1 patient during Cycle 1. If fewer than 2 of 6 patients experience a DLT during Cycle 1, patients in Cohort 2 will receive ARRY-382 400 mg QD. If 2 or more patients in Cohort 1 experience DLTs during Cycle 1, the dosage of ARRY-382 in Cohort 2 will be 100 mg QD. If a Grade 3 immune-related AE (irAE) (first occurrence) is reported in a given cohort, enrollment in that cohort will continue at the same dose until the toxicity is evaluated. If a second Grade 3 irAE is reported or a first Grade 3 irAE is reported in addition to a previous DLT in a given cohort, enrollment of new patients in that cohort will be stopped until the Grade 3 irAE is evaluated. If the event is not a DLT (as determined by the Investigators in consultation with the Sponsor), then enrollment may be resumed, or the cohort may be expanded to include up to 9 patients. If the Grade 3 irAE is deemed a DLT, the MTD has been achieved and additional patients will be enrolled at the previous dose level or at an intermediate dose level.

Intermediate doses and doses higher than 400 mg QD may also be considered upon review of the safety and PK results from the planned dose cohorts.

Table 6: Planned Dose Cohorts (Part A)

	Planned dose regimen	
	ARRY-382	Pembrolizumab
Cohort 1	200 mg po QD	2 mg/kg iv every 3 weeks
Cohort 2	If patients with DLTs \geq 2 of 6 in Cycle 1: 100 mg po QD	2 mg/kg iv every 3 weeks
	If patients with DLTs \leq 1 of 6 in Cycle 1: 400 mg po QD	2 mg/kg iv every 3 weeks

DLT = dose limiting toxicity; iv = intravenously; kg = kilogram(s); mg = milligram(s); po = by mouth; Q3W = every 3 weeks; QD = once daily

In the absence of identification of an MTD, a dose of 400 mg or lower may be selected as the RP2D as long as the DLT rate is < 33% (e.g., fewer than 2 of 6 patients experience a DLT).

Part A has been completed and the MTD/RP2D of ARRY-382 was determined to be 300 mg QD in combination with pembrolizumab. Cohorts evaluating patients with metastatic melanoma (previous Part B) and PD-L1-positive NSCLC (previous Part C) were removed by protocol amendment after enrollment of 1 patient in each cohort due to changes in the respective treatment paradigms.

Phase 2 will consist of 3 separate cohorts of patients. The Phase 2 PD-1/PD-L1 Inhibitor Refractory cohort will consist of patients with advanced solid tumors who progressed on a PD-1/PD-L1 inhibitor-containing regimen as their most recent prior line of therapy are who are naïve to prior CSF-1R or CSF-1 inhibitors. The Phase 2 prOVCA and PDA cohorts will consist of patients with prOVCA and patients with PDA, respectively, who have had at least one prior line of therapy and who are naïve to prior checkpoint inhibitor (CPI) therapy and to prior CSF-1R or CSF-1 inhibitors.

In Phase 2, at baseline, submission of archived tumor tissue from the most recent sample collection available or a fresh biopsy will be required.

All patients in Phase 2 will receive ARRY-382 at 300 mg QD, the MTD/RP2D determined during Part A, in combination with pembrolizumab 200 mg iv Q3W.

Efficacy assessments include determination of objective response using RECIST v1.1. For patients who have initial evidence of radiological progressive disease (PD) by RECIST v1.1, it will be at the discretion of the Investigator to keep a patient on study treatment or to stop study treatment until repeat imaging is performed approximately 4 weeks later in order to confirm PD per irRC. Patients with confirmed irPD should discontinue treatment. Patients with a declining Eastern Cooperative Oncology Group performance status (ECOG PS), deteriorating clinical symptoms or rapid progression of disease/progression at critical anatomical sites (i.e., central

nervous system [CNS]) should be considered for treatment discontinuation based on clinical judgment.

CCI [REDACTED]

Pharmacokinetic assessments include determination of plasma concentrations of ARRY-382 and its metabolites.

Safety assessments include monitoring of AEs, clinical laboratory tests (hematology, coagulation, clinical chemistry, thyroid panel, and urinalysis), physical examinations, vital signs, and electrocardiograms (ECGs). ECOG PS will also be assessed.

4.2 Dose-Limiting Toxicities (Part A)

For Part A, DLTs are defined as a treatment-emergent adverse event (TEAE) or abnormal laboratory value not clearly attributable to an extraneous cause, such as disease progression, intercurrent illness, or concomitant medications occurring during Cycle 1 and meeting one of the criteria shown in [Table 7](#).

Table 7: Dose-Limiting Toxicities (Part A)

Toxicity	DLT Definition Criteria
Nonhematologic AEs	
 • Recurring Grade 2 pneumonitis • Grade 3 irAE that does not resolve or return to baseline with immunosuppressive therapy within 28 days of onset • Grade 3 QTcF prolongation or > 60 msec increase in QTcF over baseline • Grade 3 rash that does not resolve or return to baseline in <10 days with symptomatic management • Any other Grade 3 or 4 nonhematologic AE, with the following exceptions: 
 ○ Alopecia ○ Grade 3 nausea, diarrhea, or vomiting lasting less than 72 hours with optimal medical management ○ Grade 3 AE of tumor flare or pseudoprogression (defined as local pain, irritation, or rash localized at sites of known or suspected tumor) ○ Grade 3 endocrinopathy that is adequately controlled by hormonal replacement
Hematology AEs/ Laboratory abnormalities	
 • Any Grade 4 hematologic AEs or Grade 4 laboratory abnormalities, with the following exceptions: 
 ○ Grade 4 lymphopenia ○ Grade 4 neutropenia lasting ≤ 48 hours that is not associated with fever or other clinically significant symptoms ○ Isolated Grade 4 electrolyte imbalances/abnormalities that are not associated with clinical sequelae and are corrected with supplementation/appropriate management within 72 hours of onset • Grade 3 thrombocytopenia with clinically significant bleeding that requires platelet transfusion • Febrile neutropenia defined as a fever with or without clinically or microbiologically documented infection with absolute neutrophil count (ANC) < 1.0 × 10⁹/L, and a fever ≥ 38.5 °C • Any Grade 4 AST or ALT elevation unless clearly attributable to disease progression • Grade 3 AST or ALT elevation lasting > 7 days unless clearly attributable to disease progression • Grade 3 AST or ALT elevation associated with bilirubin levels ≥ 2 × ULN or an international normalized ratio (INR) > 1.5 unless clearly attributable to disease progression • Any Grade ≥ 3 bilirubin elevation unless clearly attributable to disease progression • CK elevation ≥ Grade 3 lasting > 7 days OR associated with an increase in creatinine ≥ 1.5 × the baseline value for creatinine
Dose delay	
 • Interruption of dosing for greater than 14 days, if due to AEs not related to the underlying disease or intercurrent illness
Other	
 • Inability to receive at least 67% of protocol-specified doses of ARRY-382 during Cycle 1 due to AEs not related to the underlying disease or intercurrent illness

AE = adverse event; ALT = alanine aminotransferase; ANC = absolute neutrophil count; AST = aspartate aminotransferase; CK = creatine kinase; DLT = dose-limiting toxicity; INR = International Normalized Ratio; irAE = immune-related adverse event; QTcF = QT interval corrected for heart rate using Fridericia's formula; ULN = upper limit of normal

For the purposes of dose escalation and determination of the MTD in Part A, only DLTs that occur during Cycle 1 will be necessarily considered for decisions regarding dose escalation. Other clinically significant toxicities or TEAEs that meet the definition of DLT occurring after Cycle 1 (i.e., dose-modifying events) may be considered when determining the RP2D.

In Part A, patients who require a dose interruption or reduction during the initial 21-day treatment period (Cycle 1) will remain evaluable for tolerability decisions if the reason for the reduction and/or interruption represents a DLT. Patients will be replaced if they have received less than 67% dose intensity [(administered dose in mg/planned dose in mg) x 100] of ARRY-382 or if they did not receive pembrolizumab for any reason other than an AE or abnormal laboratory value that is not related to disease, disease progression, intercurrent illness or concomitant medications/therapies before completing Cycle 1.

Dose modifications of study drug are described in [Section 6.3](#).

For Part A, after the last patient in a given cohort has completed 1 cycle of study treatment, the Sponsor Medical Monitor and Investigators will meet to review all safety data and decide whether to continue or halt dose escalation, expand individual dose levels to gain additional safety data, determine the MTD and/or RP2D, or explore other dose levels. In addition to end-of cohort meetings, safety meetings including the Sponsor Medical Monitor and Investigators will be scheduled periodically (e.g., every 4 weeks) during the conduct of Phase 2 to review safety data for ongoing patients and patients who are being monitored during the follow-up period.

4.3 End of Study

End of study will be defined as the point when all patients have had the opportunity to be followed for at least 1 year after the date the last patient enrolled receives first treatment. Any patients still receiving study drugs at the end of the study will be allowed to continue at the discretion of the Investigator and as long as none of the treatment discontinuation criteria are met (see [Section 9.2](#)). The Sponsor will notify all applicable regulatory agencies in accordance with local requirements when the study has ended. After the end of the study, access to study drugs will be provided only in accordance with local regulations and requirements.

5.0 PATIENT POPULATION

This clinical study can fulfill its objectives only if appropriate patients are enrolled. The eligibility criteria described in this study protocol are designed to identify patients for whom treatment is considered appropriate. All relevant medical and nonmedical conditions should be considered when deciding whether a patient is suitable for enrollment in the study.

5.1 Number of Patients

Overall, approximately 90 patients at approximately 30 study sites are planned for enrollment.

Part A (Phase 1b) will consist of approximately 18 patients with selected solid tumors.

The Phase 2 PD-1/PD-L1 Inhibitor Refractory cohort will consist of up to 20 patients with advanced solid tumors who progressed on a PD-1/PD-L1 inhibitor-containing regimen as their most recent prior line of therapy. If clinical activity is observed, enrollment may be focused to include up to 10 additional patients with particular tumor histologies of interest.

The Phase 2 prOVCA cohort will consist of approximately 23 patients with prOVCA who are naïve to prior CPI therapy. The Phase 2 PDA cohort will consist of approximately 29 patients with PDA who have had at least one prior therapy who are naïve to prior CPI therapy.

5.2 Selection of Patients

Questions regarding patient eligibility should be addressed with the Sponsor prior to enrollment of a particular patient. Patients must fulfill all of the following inclusion criteria and none of the exclusion criteria to be eligible for admission to the study.

5.2.1 Inclusion Criteria

1. Personally signed and dated informed consent form
2. Male or female \geq 18 years of age
3. Diagnosis of cancer that has been histologically or cytologically confirmed as follows:

Part A (1 of the following):

- a. Ovarian cancer, triple-negative breast cancer, HNSCC, bladder cancer, metastatic CRC, PDA, or gastric cancer that is measurable or evaluable, nonmeasurable as defined by RECIST v1.1 and meets 1 of the following criteria:
 - is refractory to standard of care

- no standard therapy available
- patient refuses standard therapy
- b. Advanced, unresectable, or metastatic melanoma with or without prior treatment and measurable or evaluable, nonmeasurable disease as defined by RECIST v1.1
- c. Advanced/metastatic PD-L1–positive NSCLC (defined as TPS \geq 50%) with measurable or evaluable, nonmeasurable disease as defined by RECIST v1.1 (1 of the following):
 - 1) Patients with metastatic PD-L1 positive NSCLC with no EGFR or ALK genomic tumor aberrations and no prior systemic chemotherapy
 - 2) Patients with advanced/metastatic PD-L1 positive NSCLC with disease progression on or after platinum-containing chemotherapy
 - 3) Patients with advanced/metastatic PD-L1 positive NSCLC with EGFR or ALK genomic tumor aberrations, with disease progression on FDA-approved therapy for these aberrations

All patients with NSCLC must provide documentation of positive PD-L1 expression, defined as a TPS \geq 50% on a fresh tumor biopsy (preferred) or the most recent archived tumor sample available. If test results documenting positive PD-L1 expression were not obtained using an FDA-approved test, then tumor tissue must be submitted to a central laboratory and it will be tested retrospectively using an FDA-approved test at a central laboratory (please see the laboratory manual for additional details).

Phase 2 (1 of the following):

- a. Advanced/metastatic solid tumor with PD as defined by RECIST 1.1 or irRC on an anti-PD-1- or anti-PD-L1-containing regimen as their most recent prior therapy
 - b. Advanced/metastatic epithelial ovarian cancer, peritoneal cancer or tubal cancer with measurable disease as defined by RECIST 1.1, that had progressed within 6 months of completing \geq 4 cycles of platinum-based therapy
 - c. Advanced/metastatic PDA that is locally advanced, unresectable or metastatic with measurable disease as defined by RECIST v1.1 in patients who have received at least one prior line of systemic therapy for their disease
4. Eastern Cooperative Oncology Group Performance Status of 0 or 1 (see [APPENDIX 1](#))
5. Adequate bone marrow function at screening, characterized by the following:
- a. absolute neutrophil count (ANC) \geq $1.0 \times 10^9/L$

- b. platelets $\geq 75 \times 10^9/L$
 - c. hemoglobin ≥ 9.0 g/dL
Note: Transfusions will be allowed to achieve the acceptable hemoglobin value.
6. Adequate renal function characterized by serum creatinine $\leq 1.5 \times$ upper limit of normal (ULN) or calculated or directly measured creatinine clearance ≥ 50 mL/min at screening
 7. Adequate hepatic function at screening, characterized by the following:
 - a. serum total bilirubin $\leq 1.5 \times$ ULN and < 2 mg/dL
Note: Patients who have a total bilirubin level $> 1.5 \times$ ULN will be allowed if their indirect bilirubin level is $\leq 1.5 \times$ ULN
 - b. ALT and/or AST $\leq 2.5 \times$ ULN, or $\leq 5 \times$ ULN in presence of liver metastases
 8. For male patients and female patients of childbearing potential, agreement to use an acceptable method of contraception as defined in the protocol (see [Section 5.3](#)) from the start of study treatment until 7.5 months after the last dose of pembrolizumab for males and until 5.5 months after the last dose of pembrolizumab for females
Note: Women are considered not of childbearing potential if they have had 12 months of natural (spontaneous) amenorrhea with an appropriate clinical profile (e.g., age appropriate, history of vasomotor symptoms) or have had surgical bilateral oophorectomy with hysterectomy or tubal ligation at least 6 weeks prior to Screening. In the case of oophorectomy alone, only when the reproductive status of the woman has been confirmed by follow-up hormone level assessment is she considered not of childbearing potential.
 9. For females of childbearing potential only, negative serum human chorionic gonadotropin (hCG) pregnancy test result at baseline and nonlactating
 10. Willingness and ability to comply with scheduled visits, treatment plan, laboratory tests, and other study procedures
 11. **Phase 2 only:** Availability of a fresh biopsy (preferred) or an archival tumor sample from the most recent sample available. Between 10 to 15 slides or an archival block are required.

This requirement may be waived under certain circumstances (e.g., sufficient archived tissue is no longer available and fresh specimen collection is deemed medically unsafe or not feasible by the Investigator due to the location of the tumor) after discussion and agreement between the Sponsor and the Investigator.

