AE = adverse event; AUC_{τ} = area under the plasma concentration-time curve over the dosing interval; C_{max} = maximum observed plasma concentration; CSF-1 = colony-stimulating factor 1; CTCAE = Common Terminology Criteria for Adverse Events; C_{trough} = plasma concentration measured just before the next dose of study drug; CCI [REDACTED]; DLT = dose-limiting toxicity; DOR = duration of response; FDA=United States Food and Drug Administration; irRC = immune-related response criteria; irRR = immune-related response rate; irPFS = immune-related progression-free survival; MTD = maximum tolerated dose; NCI = National Cancer Institute; CCI [REDACTED] ORR = objective response rate; OS = overall survival; CCI [REDACTED] 1; PFS = progression-free survival; PK = pharmacokinetic(s); RECIST, v1.1 = Response Criteria in Solid Tumors, version 1.1; RP2D = recommended Phase 2 dose; SAE = serious adverse event; T_{max} = time of maximum observed plasma concentration; CCI [REDACTED]

3.2 Phase 2

Objectives and endpoints for the Phase 2 portion of the study are presented in [Table 3](#) for the PD-1/PD-L1 Inhibitor Refractory cohort, in [Table 4](#) for the prOVCA cohort and in [Table 5](#) for the PDA cohort.

Table 3: Objectives and Endpoints (Phase 2: PD-1 or PD-L1 Inhibitor Refractory)

Primary Objective	Primary Endpoint
To estimate the efficacy of ARRY-382 in combination with pembrolizumab in patients with advanced solid tumors following progression on prior PD-1/PD-L1 inhibitor therapy	ORR, per RECIST v 1.1, as determined by the Investigator
Secondary Objectives	Secondary Endpoints

 To further estimate the efficacy of the combination 	
 DOR, per RECIST v1.1, as determined by the Investigator PFS, per RECIST v1.1, as determined by the Investigator irRR, per irRC, as determined by the Investigator irPFS, per irRC, as determined by the Investigator OS

 To characterize the safety and tolerability of the combination, including acute and chronic toxicities 	
 Type, frequency, and severity of AEs, using the NCI CTCAE SAEs, using the NCI CTCAE Clinical laboratory values Vital signs

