#### Phase 2: PD-1 or PD-L1 Inhibitor Refractory:

- Objective response rate (ORR), per RECIST v 1.1, as determined by the Investigator

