- Progression >9 weeks after the start of treatment (i.e. tumor assessment of PD was >9 weeks after start of treatment and there was no tumor assessment in between)

Special (and rare) cases where BOR is 'Not evaluable' due to both SD occurring  $\leq$  6 weeks after start of treatment and progression > 9 weeks after the start of treatment will be classified as "SD occurred  $\leq$  6 weeks after the start of treatment".

The ORR will be calculated with an exact two-sided 95% CI. The 95% CI will be derived using the Clopper-Pearson exact binomial CI method. In addition, the number and percentage of patients in each BOR category (i.e., CR, PR, stable disease (SD), progressive disease (PD), and Not Evaluable) will be summarized.

A figure for duration of exposure and best overall response (confirmed) will be created.

A waterfall plot will be created to show the best percentage change from the baseline in the sum of longest diameters. Patients with baseline and at least one post-baseline tumor assessment will be included in the waterfall plot.

Individual lesion measurements and overall response assessments per RECIST v1.1 will be listed by patient and assessment date.

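### The PD-1/PD-L1 refractory cohort is judged on RECIST ORR in all treated patients, but its eligibility criterion does not require measurable disease, so ORR can be biased downward

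*Protocol*

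**What the plan says.** Protocol Section 5.2.1, criterion 3, sets one disease criterion for each Phase 2 cohort.

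- **3a, refractory:** "Advanced/metastatic solid tumor with PD as defined by RECIST 1.1 or irRC", where the progression was on a PD-1 or PD-L1 inhibitor regimen given as the latest prior treatment. Measurability is not mentioned.
- **3b, platinum-resistant ovarian:** "peritoneal cancer or tubal cancer with measurable disease as defined by RECIST 1.1".
- **3c, pancreatic:** "locally advanced, unresectable or metastatic with measurable disease as defined by RECIST v1.1".

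The Part A criteria in the same section expressly accept both measurable and evaluable non-measurable disease. Criterion 3a says neither.

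The refractory cohort's primary endpoint is "ORR, per RECIST v 1.1, as determined by the Investigator" (Protocol Table 3). SAP Section 4.1 repeats it: "Objective response rate (ORR), per RECIST v 1.1, as determined by the Investigator". SAP Sections 5.3 and 7.5 place all efficacy analyses on the full analysis set (FAS), meaning everyone who received at least one dose of either drug. SAP Section 7.5.1 adds an exact 95% interval and a table of "the number and percentage of patients in each BOR category", with the categories CR, PR, SD, PD and Not Evaluable. It plans no analysis restricted to patients with target lesions.

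**The concern.** Under Protocol Appendix 5, PR is a decrease of at least 30% in the sum of target-lesion measures, so it needs at least one target lesion. A cohort whose primary endpoint is CR plus PR would therefore normally require measurable disease, as the other two Phase 2 cohorts do. Without that requirement, the denominator can include patients who have one route to response instead of two. The estimate then mixes the activity of the combination with the share of patients in whom PR could not be observed.

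The cohort is there to look for initial evidence of activity in about 20 patients, without a null or target rate. The observed ORR and its interval are its main result, so a downward bias falls directly on that result.

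**Working it through.** **1. Is measurable disease required anywhere else for this cohort?** No. The other inclusion and exclusion criteria (Protocol 5.2.1 and 5.2.2), the design overview (4.1), the patient numbers (5.1) and the efficacy assessments (7.2, 7.2.1) do not add it.

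**2. Does prior progression guarantee a RECIST target lesion?** Criterion 3a accepts progression by either of two systems.

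- *RECIST v1.1 (Appendix 5, Section 1.1.5):* new lesions alone constitute PD, and unequivocal non-target progression may be accepted in exceptional circumstances. Neither needs a measurable lesion.
- *irRC (Appendix 6):* this route is narrower. Progression needs a rise of at least 25% in measured tumor burden. New non-measurable lesions do not define it, and non-index progression alone is at most irSD. But new lesions count from 5 x 5 mm, whereas RECIST measurability on CT starts at 10 mm (15 mm short axis for nodes; Appendix 5, Section 1.1.1).

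Neither route guarantees a RECIST target lesion at baseline.

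**3. What can such a patient score?** The non-target-only block of Appendix 5, Table 1 gives CR, Non-CR/non-PD, NE or PD. It has no PR row.

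**4. Does the patient stay in the denominator?** Yes, because the FAS has no measurability condition. The general rule in SAP 7.1.7 that percentages use patients with an observation does not remove them, since they do have time-point assessments.

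**5. Size.** The documents state no rate, alpha, power or decision count for this cohort, so there is no planned figure to reproduce. Two quantities have to be assumed:

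- p, the true ORR in patients with measurable disease;
- m, the number of the 20 without measurable disease, taken to have no CRs.

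Expected FAS ORR = p x (20 - m)/20. Each such patient removes 1/20, or 5%, of the value of p. For example, with p = 15% and m = 2: 15% x 18/20 = 13.5%.

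| m | p = 10% | p = 15% | p = 20% |
|---|---|---|---|
| 0 | 10.0% | 15.0% | 20.0% |
| 1 | 9.5% | 14.25% | 19.0% |
| 2 | 9.0% | 13.5% | 18.0% |
| 4 | 8.0% | 12.0% | 16.0% |
| 6 | 7.0% | 10.5% | 14.0% |

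**6. What a reader would see.** Suppose three responses are observed, all in patients with target lesions. Exact (Clopper-Pearson) 95% intervals:

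| Denominator | ORR | 95% CI |
|---|---|---|
| FAS, 20 | 3/20 = 15.0% | 3.2 to 37.9% |
| Target lesion present, m = 2 | 3/18 = 16.7% | 3.6 to 41.4% |
| Target lesion present, m = 4 | 3/16 = 18.8% | 4.0 to 45.6% |

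**7. Tabulation.** Non-CR/non-PD has no place among the SAP's BOR categories. Read literally, it falls into the residual Not Evaluable group, and none of the listed reasons for that status describes a patient who was assessed but had no target lesion. Such a patient is a non-responder under either label, so ORR does not change.

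**The case against.** The strongest case against acting is that this is a wording asymmetry in a small cohort meant for estimation. Several parts of that case stand.

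- **Version.** SAP Section 1.0 says it was developed from protocol Version 5, dated 02 January 2019. The protocol supplied is Version 4. The SAP does not restate the eligibility criteria, so 3a may already have been changed. The eligibility half of the fix has to be conditional on that.
- **Size.** The shifts in the interval table are small against the interval widths. An all-treated denominator is also conservative: the bias is downward and cannot create a false claim of activity.
- **Recoverability.** SAP 7.5.1 lists individual lesion measurements by patient, so the restricted ORR could be derived later. Prespecifying it is still better than choosing the denominator after the responses are known.

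Some stronger readings are tempting, and the documents do not support them.

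- *These patients cannot respond.* They can, through CR.
- *The cohort loses power.* It has no test, and any minimum response count chosen to show a loss would be invented.
- *ORR decides the expansion.* Protocol Section 5.1 says only that enrollment of up to 10 more patients may be focused on histologies of interest if clinical activity is seen. Clinical activity is not defined there or tied to the FAS ORR.
- *Comparison with the other cohorts is spoiled.* None is planned, and the cohorts already differ in histology and prior checkpoint-inhibitor exposure.

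**Conclusion.** The point holds, with modest consequences. As written in Version 4 and the SAP, patients who cannot have a PR may enter the refractory cohort and would count in the denominator of its primary endpoint. The direction of the bias is certain, provided the CR rate in such patients is below the ORR of those with measurable disease. Its size is unknown: the documents neither show that any such patient was enrolled nor give a rate for patients with measurable disease. Under the no-CR assumption it is 5% of the ORR's value per patient among 20. The stated operating characteristics all belong to the other parts of the study and are untouched. A low-cost correction is worth making. The BOR category gap is a separate, minor tabulation matter.

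**What to change.** 1. **Eligibility.** Check criterion 3a in protocol Version 5. If it is unchanged, add a requirement for RECIST v1.1 measurable disease, in the same terms as 3b and 3c, for any further enrolment.
2. **SAP Section 7.5.1.** Keep the FAS ORR as the primary analysis. For the refractory cohort, also report ORR with its exact 95% CI in patients with at least one target lesion at baseline, and state how many patients had none. This is useful even if enrolment is complete, because the SAP is to be finalized before database lock.
3. **BOR table.** Add Non-CR/non-PD as a category. This does not affect ORR.

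The cost is one eligibility phrase, slightly fewer eligible patients, one extra table line and one extra category. No patient leaves the FAS analysis.
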